23.0 BACKGROUND INFORMATION

23.1 COVID-19 Vaccination in Immuno-Suppressed Cancer Patients

Are immuno-suppressed individuals, including those treated for cancer, adequately protected from SARS-CoV-2 mediated disease post-administration of an FDA Emergency Use Authorization (EUA) or approved COVID-19 vaccine regimen?

In the development of EUA or approved vaccines for COVID-19, immune compromised people and those on immunosuppressant therapies were not systematically enrolled or evaluated for safety and effectiveness of the study vaccine agent. Importantly, this includes patients with a history of cancer who were on active treatment for their disease (chemotherapy, immunotherapy, targeted therapy, any combination of drug therapies, radiation therapy).

This is especially important since patients treated for either solid tumors or hematologic malignancy may not be able to mount the robust vaccine mediated antibody and/or cellular immune responses needed to provide protection against the consequences of potentially life-threatening SARS-CoV-2 infection. These patients are at increased risk of severe illness from SARS-CoV-2.

- In a CDC study of 73 million patients in the USA of whom 273,000 had been diagnosed with cancer in the last year and 16,570 were diagnosed with COVID-19, patients with cancer had greatly increased odds of SARS-CoV-2 infection (adjusted odds ratio [aOR] of 7). Odds of infection were highest for patients with recently diagnosed leukemia (aOR 12.2), non-Hodgkin's lymphoma (aOR 8.5), and lung cancer (aOR 7.7). Mortality was also higher in patients with cancer who developed COVID-19. Indeed, patients with cancer and COVID-19 had a significantly greater risk of mortality (14.9%) than patients with COVID-19 without cancer (5.3%) and patients with cancer without COVID-19 (4.0%).
- For patients diagnosed with a hematologic malignancy in the last 5-years, the increased risk of death has been estimated to be at least 2.5-fold.

Clearly, there is a critical unmet clinical need for protective treatment in immuno-suppressed (i.e., high risk) patients for SARS-CoV-2 infection and subsequent progression to severe pulmonary disease complications including hospitalization or death. The following table

summarizes several recent clinical evaluations conducted in potentially immuno-suppressed patients with either a history of cancer or organ transplant.

SAR-CoV-2 Antibody Response to COVID-19 Vaccine Dosing in Cancer or Organ Transplant Patients

REF	Patient Population	# Pts	Vaccine	Antibody Testing	Results	Comments
Lancet Heme	• Myeloma	93	• Oxford AZ • PFE-BioNTech	• ≥3 weeks post 1 st dose • No f/u post 2 nd dose.	• Only 13% of myeloma patients had detectable Ab response at ≥3 weeks post 1 st vaccination	• No control group.
Tel Aviv Sourasky Med. Ctr. in Israel	• Chronic Lymphocytic leukemia (N=167) • Healthy Controls (N=52)	219	• PFE-BioNTech (100%)	• All CLL and healthy Controls received 2 doses of the Pfizer vaccine approx. 3 weeks post 2 nd dose.	• For the 167 CLL pts, 39.5% were Ab positive. • A comparison of 52 CLL and 52 healthy Controls showed 52% Ab positive for CLL pts and 100% Ab pos. for Controls. (p<0.001) • In CLL patients, Ab positive results were: ▪ 16% if currently under treatment ▪ 55.2% if treatment-naïve ▪ 79.2% if obtained clinical remission	• Several weeks after administration of the 2 nd dose of PFE- BioNT vaccine, CLL patients continue to have reduced Ab positive response.
London School of Hygiene & Tropical Medicine	• 151 elderly pts with solid cancers (e.g., breast, prostate, heme cancers) and 54 healthy Controls	205	• PFE-BioNTech (100%)	• ≥3 weeks post 1 st dose • 3 wks post 2 nd dose in limited number of patients.	• 3 weeks after 1 st dose, 39% of solid cancer pts and 13% of blood cancer pts had pos. Ab. 97% of Controls were Ab positive. • 5 weeks after dose #1, 43% of solid cancer pts and 8% of blood cancer pts had a positive Ab response. 100% of Controls were Ab pos. • 2 weeks after dose #2 (if given), Ab response was 95% in solid cancer pts. Insufficient data for blood cancer patients.	• Post dose 1 of Pfizer vaccine in immuno-compromised pts, most solid and heme cancer pts remained immunologically unprotected up until a least 5 weeks post the primary injection.
JAMA, Hopkins	• Kidney, liver or heart transplant. No prior COVID-19 or positive SARS-CoV-2 Ab. • Median age 55.9 yrs. • Median time since organ Tx was 6.2 yrs.	436	• Moderna (48%) • PFE/BioNTech (52%)	• Median of 20 days after dose 1.	• 17% of Transplant pts had detectable Ab at a median of 20 days after dose 1. • 8% had detectable Ab if on an anti-metabolite like MMF or azathioprine	• Organ transplant pts have a high level of immunosuppression relative to COVID-19 Ab production. • Ab response most likely in pts <60 y.o.

23.2 COVID-19 Antibody Production

- It is assumed that immune competent, non-cancer patients who are vaccinated with either a single-dose or two-doses of a COVID-19 EUA or approved vaccine will produce antibodies to the SARS-CoV-2 spike protein at 4 weeks after complete vaccination. It is unclear if the EUA or approval for the Pfizer, Moderna or Janssen vaccines included a large enough cohort of cancer patients to statistically determine if they produced spike protein antibodies and if their antibody levels were comparable to age and gender-matched patients who did not have cancer. This is the dilemma for treated cancer patients: Does their current chemotherapy, immunotherapy, targeted therapy, other therapy, combination therapy and/or radiation therapy prevent them from making antibodies to a level similar to that seen in non-cancer patients?
- Is it possible that cancer patients cannot make antibodies at all or that their level of antibody production is lower than that observed in non-cancer patients?

If so, can administration of a combination of two, long-acting, monoclonal antibodies provide protection against symptomatic SARS-CoV-2 infection as well as COVID-19 related hospitalization and/or COVID-19 related death?

These questions define the challenge and ultimate goal of this study.

23.3 Additional Dose of Covid-19 EUA Vaccine

The FDA has recently announced that patients who are considered immuno-compromised, such as treated cancer patients, whether they did or did not produce antibodies to SARS-CoV-2 spike protein (RBD-IgG) following their initial vaccination regimen with either the Pfizer, Moderna or Janssen vaccine will be permitted and encouraged to receive an additional dose of COVID-19 vaccine from either Pfizer, Moderna or Janssen. As a result of the recent FDA decision, patients may now receive the additional dose from either the same vaccine manufacturer that provided their original vaccination or from another FDA approved manufacturer (i.e., Janssen original and then Moderna additional). It is intended that this additional dose will provide protection against complications from SARS-CoV-2 infection. The fact remains that without quantitating the RBD-IgG, it is unknown whether this vaccination protocol will be protective for cancer patients.

23.4 AZD7442

AZD7442 (Evusheld) is a combination of two long-acting antibodies (LAABs) - tixagevimab (AZD8895) and cilgavimab (AZD1061) - derived from B-cells donated by convalescent patients after SARS-CoV-2 virus. Discovered at Vanderbilt University Medical Center and licensed to AstraZeneca in June 2020, the human monoclonal antibodies bind to distinct sites on the SARS-CoV-2 spike protein and were engineered and optimized by AstraZeneca with half-life extension and reduced Fc receptor and complement C1q binding. The half-life extension more than triples the durability of its action compared to conventional antibodies and could afford up to 12 months of protection from SARS-CoV-2 infection following a single administration. The reduced Fc receptor binding aims to minimize the risk of antibody-dependent enhancement of disease - a phenomenon in which virus-specific antibodies promote, rather than inhibit, infection and/or disease.

Data published in [*Nature*](#) in July 2020 showed in preclinical experiments that LAABs were able to block the binding of the SARS-CoV-2 virus to host cells and protect against infection in cell and animal models of disease.

23.5 AZD7442 Clinical Trial Results:

- AZD7442 is being studied in a comprehensive clinical trial program for both prevention and treatment of SARS-CoV-2 infection in over 9,000 participants. Ongoing trials include **TACKLE COVID-19**, a Phase III treatment trial in an outpatient setting and collaborator treatment trials in outpatient and hospitalized settings. **TACKLE** included 903 participants in a 1:1 randomization AZD7442 to placebo. AZD7442 is the first LAAB with Phase III data to demonstrate benefit in both prophylaxis and treatment of SARS-CoV-2 infection and is easily administered by IM injection. 90% of enrolled participants were from populations at high risk of progression to severe COVID-19, including those with co-morbidities. The primary analysis was based on 822 participants.
- AZD7442 was assessed using both IM and IV administration routes. Positive high-level results from the **TACKLE** Phase III COVID-19 treatment trial showed AstraZeneca's AZD7442, a long-acting antibody (LAAB) combination, achieved a statistically significant reduction in severe SARS-CoV-2 infection or death compared to placebo in non-hospitalized patients with mild-to-moderate symptomatic SARS-CoV-2 infection.
- The trial met the primary endpoint, with a dose of 600mg of AZD7442 given by intramuscular (IM) injection reducing the risk of developing severe SARS-CoV-2 infection or death (from any cause) by 50% compared to placebo in outpatients who had been symptomatic for seven days or less. The trial recorded 18 events in the AZD7442 arm (18/407) and 37 in the placebo arm (37/415). The LAAB was well tolerated in the trial.
- In a prespecified analysis of participants who received treatment within five days of symptom onset, AZD7442 reduced the risk of developing severe SARS-CoV-2 infection or death (from any cause) by 67% compared to placebo, with nine events in the AZD7442 arm (9/253) and 27 in the placebo arm (27/251).
- AstraZeneca has submitted a request to the US Food and Drug Administration (FDA) for Emergency Use Authorization (EUA) for AZD7442, its long-acting antibody (LAAB) combination, for prophylaxis of symptomatic SARS-CoV-2 infection. The EUA request filing includes safety and efficacy data from the **PROVENT** and **STORM CHASER** Phase III trials and the Phase I trial. AZD7442 was optimized using

AstraZeneca's proprietary YTE half-life extension technology which more than triples the durability of its action compared to conventional antibodies.

- Preliminary 'in vitro' findings demonstrate that AZD7442 has broad anti-COVID activity, and in particular neutralizes recent emergent SARS-CoV-2 viral variants, including Delta and Mu variants.
- In June 2021, AstraZeneca announced results from the STORM CHASER trial assessing the safety and efficacy of AZD7442, a long-acting antibody (LAAB) combination, for the prevention of symptomatic SARS-CoV-2 infection in participants recently exposed to the SARS-CoV-2 virus. The trial did not meet the primary endpoint of post-exposure prevention of symptomatic SARS-CoV-2 infection with AZD7442 compared to placebo.
- Trial participants were unvaccinated adults 18 years and over with confirmed exposure to a person with a case of the SARS-CoV-2 virus within the past eight days. In the overall trial population, AZD7442 reduced the risk of developing symptomatic COVID-19 by 33% (95% confidence interval (CI): -26, 65) compared to placebo, which was not statistically significant.
- The trial included 1,121 participants in a 2:1 randomization AZD7442 to placebo, with 23 cases of symptomatic SARS-CoV-2 infection accrued in the AZD7442 arm (23/749) and 17 cases accrued in the placebo arm (17/372). All participants had a negative SARS-CoV-2 antibody test on the day of dosing to exclude prior infection, and a nasopharyngeal swab was also collected and subsequently analyzed for SARS-CoV-2 by RT-PCR to detect virus.
- Given the importance of finding therapies for SARS-CoV-2 infection and to help interpret trial results during the pandemic, additional analyses were performed and are being communicated.
- In a pre-planned analysis of SARS-CoV-2 PCR positive (detectable virus) and PCR negative (no detectable virus) participants in the STORM CHASER trial, AZD7442 reduced the risk of developing symptomatic SARS-CoV-2 infection by 73% (95% CI: 27, 90) compared with placebo, in participants who were PCR negative at time of dosing. In a post-hoc analysis, in participants who were PCR negative at baseline, AZD7442 reduced the risk of developing symptomatic SARS-CoV-2 infection by 92%

(95% CI: 32, 99) versus placebo more than seven days following dosing, and by 51% (95% CI: -71, 86) up to seven days following dosing.

- In August 2021, AstraZeneca announced preliminary results from the PROVENT pre-exposure prophylaxis trial which showed AZD7442 reduced the risk of developing symptomatic SARS-CoV-2 infection by 77% (95% confidence interval (CI): 46, 90), compared to placebo. Importantly, the trial population included people with co-morbidities and who may be in need of additional protection from SARS-CoV-2 infection. Greater than 75% of participants in PROVENT presented with co-morbidities associated with an increased risk of severe disease or a reduced immune response to vaccination. The trial accrued 25 cases of symptomatic SARS-CoV-2 infection at the primary analysis. AZD7442 was well-tolerated.
- On December 8, 2021, AZD7442 (Evusheld) received initial emergency use authorization (EUA) in the US for the pre-exposure prophylaxis (prevention) of SARS-CoV-2 infection. The Food and Drug Administration (FDA) granted the EUA for AZD7442 for pre-exposure prophylaxis of SARS-CoV-2 infection in adults and adolescents (aged 12 and older who weigh 40kg or more) with moderate to severe immune compromise due to a medical condition or immunosuppressive medications and who may not mount an adequate immune response to SARS-CoV-2 vaccination, as well as those individuals for whom SARS-CoV-2 vaccination is not recommended. Recipients should not be currently infected with or had recent known exposure to a person infected with SARS-CoV-2. As a result of the prevalence of the omicron variants BA.1 and BA.1.1, the EUA was revised and updated on February 24, 2022 to increase the dose of AZD7442 (Evusheld) from 300 mg IM to 600 mg IM.
- AZD7442 is the only antibody therapy authorized in the US for SARS-CoV-2 pre-exposure prophylaxis and the only SARS-CoV-2 antibody delivered as an intramuscular dose (300 mg tixagevimab and 300 mg cilgavimab). About seven million people in the US are immunocompromised and may benefit from AZD7442 for pre-exposure prophylaxis of SARS-CoV-2 infection. This includes people with blood cancers or other cancers being treated with chemotherapy, and those taking medications after an organ transplant or who are taking immunosuppressive drugs for conditions including multiple sclerosis and rheumatoid arthritis.

- The primary data supporting the AZD7442 EUA are from the ongoing PROVENT Phase III pre-exposure prevention trial, which showed a statistically significant reduction (77% at primary analysis, 83% at median six-month analysis) in the risk of developing symptomatic SARS-CoV-2 infection compared to placebo, with protection from the virus continuing for at least six months. Data from the Phase III STORM CHASER post-exposure trial and the AZD7442 Phase I trial also supported the EUA.
- AZD7442 (Evusheld) has demonstrated reduced neutralization activity against the Omicron BA.1 variant (which is B.1.1.529), with a 132- to 183-fold reduction in neutralization activity seen in pseudotyped virus-like particle (VLP) assays and a 12- to 30-fold reduction in neutralization activity seen in authentic virus assays. Likewise, AZD7442 (Evusheld) demonstrated reduced neutralization activity against the Omicron BA.1.1 variant (which comprised 57% of circulating variants in the United States in the week ending 3/19/22 per <https://covid.cdc.gov/covid-data-tracker/#variant-proportions>), with a 424-fold reduction in neutralization activity seen in VLP assays and a 176-fold reduction in neutralization activity seen in authentic virus assays. Neutralization activity of AZD7442 (Evusheld) against the Omicron BA.2 variant is minimally impacted.
- Of the Omicron binding site substitutions relevant to AZD7442 that have been tested to date in preclinical assays, none have been associated with escape from AZD7442 neutralization. In vitro findings demonstrate that AZD7442 neutralizes other emergent SARS-CoV-2 viral variants, including the Delta and Mu variants.
- As of June 28, 2022 the EUA for AZD7442 has been modified and the dosing interval for AZD7442 has been adjusted to a repeat dosing of 600 mg IM or IV 6 months after the initial dose.

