- For patients not on active oral, IM or IV therapy at the time of enrollment, previous treatments may have been initiated at any time prior to treatment inactivity but must meet the hematologic or solid tumor post treatment requirements stated above
- Concomitant radiation therapy is permitted but cannot be the sole therapy
- Have been vaccinated with one or more doses of Janssen, Moderna or Pfizer COVID-19 vaccine at least 14 days prior to Baseline

- If having been previously diagnosed with SARS-CoV-2 infection, the diagnosis has to be at least 90 days prior to study randomization. If previously diagnosed, previous treatment with Ivermectin or hydroxychloroquine is acceptable.
- Have a negative SARS-CoV-2 antigen rapid test performed in the office at screening
- Patient willing to receive treatment with AZD7442 600 mg IM or IV
- Patient willing to complete baseline and 14 post-enrollment Patient Experience/Clinical Outcome Assessment surveys.
- Patient willing to complete baseline (Day 2) and 5 follow-up QoL assessments
- Patient willing to have blood drawn for serum concentration of AZD7442 5 times post-baseline and repeated if patient becomes COVID-19 positive
- Patient willing to have blood drawn for T-cell assay at day 30 and at day 210 post-baseline and repeated if patient becomes SARS-COV-2 RNA by RT-PCR positive
- Patient willing to have RBD-IgG drawn at baseline, days 90, 180, 270 and 360 post-baseline and repeated if patient becomes SARS-COV-2 RNA by RT-PCR positive
- Patient willing to signed Informed Consent Form
- Patient willing to sign Authorization for Release of Health Information (including treating physicians' or other medical personnel's records, medication prescriber records, pharmacy records and medical insurance claims)

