8.2 Exclusion Criteria

Patients meeting any of the following criteria will be excluded from study participation:

- Women who are pregnant, breast feeding or of child bearing potential and not using contraception
- Absence of a qualifying type of cancer as defined by standard ICD-10 diagnostic criteria
- Patient receiving only radiation therapy
- Patient with an ECOG performance status of 2 or higher

- Patient with an expected cancer survival of less than 12 months by disease category
- Patient receiving adjuvant endocrine therapy as their only form of therapy for early-stage breast cancer
- Solid tumor patients more than 6 months post treatment and their cancer is considered to be stable or in remission as determined by the Investigator
- AZD7442 administration at any time prior to day of enrollment
- Have a positive test for SARS-CoV-2 antigen performed by either Rapid Test or SARS-CoV-2 RNA by RT-PCR (Polymerase Chain Reaction) less than 90 days prior to enrollment
- Patient with a prior (within 90 days), current, or planned use of any of COVID-19 convalescent plasma, other monoclonal antibodies against SARS-CoV-2 or any other EUA approved SARS-CoV-2 treatment
- Patient with fever >100.0 F, and/or cough, chills, loss of smell or taste or shortness of breath or any other signs or symptoms consistent with COVID-19 within 5 days prior to enrollment
- Patient who has any known active acute respiratory infection
- Patient who has persistent (refractory to treatment for ≥ 14 days) bacterial or fungal infection
- Patient who has a past SARS-CoV-2 infection within 90 days prior to randomization
- Patient who has received vaccination with any dose of Janssen, Pfizer or Moderna COVID-19 vaccine less than 14 days prior to baseline for this study
- Planned use of any investigational, authorized, or approved vaccine for COVID-19 less than 14 days prior to administration of AZD7442 600 mg IM or IV
- Patient who is unwilling to have SARS-CoV-2 RBD-IgG antibody levels drawn at least 5 times
- Patient who is unwilling to receive treatment with IM or IV AZD7442
- Patient who is unwilling to complete baseline and up to 14 follow-up Experience/Clinical Outcome Assessment (COA) surveys.

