- Once blood is obtained for SARS-CoV-2 RBD-IgG, the patient may proceed to the Baseline Visit and be offered treatment with AZD7442. The SARS-CoV-2 specific RBD-IgG level is without charge to the patient.
- Site personnel will perform a nasal or buccal SARS-CoV-2 rapid antigen test in the office at the time of screening. If the SARS-CoV-2 rapid antigen test is negative, the patient may proceed to the baseline visit. If the SARS-CoV-2 rapid antigen test is positive, the patient will be referred for SARS-CoV-2 by RT-PCR test. If the RT-PCR test is positive, the patient is disqualified from study participation. If the SARS-CoV-2 by RT-PCR test is negative the patient may proceed to the baseline visit.
- Patients will digitally sign and site personnel will witness the Informed Consent Form (ICF)
- Site personnel will obtain CBC (including platelet count) if not performed within prior 30 days
- Patients will digitally sign Authorization for Release of Healthcare Records Form.

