12.1 Program Product Dosage and Administration

- AZD7442 600 mg (6.0 ml) dose for all participants will be provided by AstraZeneca and distributed to all sites from a central location.
- AZD7442 will be administered by all AISP participating locations according to protocol guidelines.
- AZD7442 600 mg IM will be administered according to FDA approved guidelines for administration.
- AZD7442 600 mg IV will be administered only according to the instructions in Section 9.2 of this protocol.

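### Exposure before dosing is never recorded and breakthroughs have no minimum time after the dose, so infections already incubating at the first dose count as AZD7442 breakthroughs

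*Protocol*

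**What the plan says.** Section 23.5 describes the emergency use authorization and states: "Recipients should not be currently infected with or had recent known exposure to a person infected with SARS-CoV-2". It does not define recent.

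Section 8.1 requires: "Have a negative SARS-CoV-2 antigen rapid test performed in the office at screening". Section 8.2 excludes patients with fever, cough, other listed symptoms "or any other signs or symptoms consistent with COVID-19 within 5 days prior to enrollment", a known active acute respiratory infection, or a positive test or infection in the previous 90 days. Neither list mentions contact with an infected person.

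Section 9.1 sets the order of testing: "If the SARS-CoV-2 rapid antigen test is negative, the patient may proceed to the baseline visit". A positive antigen test leads to RT-PCR, and a patient who is then RT-PCR negative may also proceed.

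Section 14.1 counts infections over 12 months from baseline and time to first event from treatment. Section 17.8 takes RT-PCR positives at any time after baseline. Section 17.10 defines a breakthrough by a positive RT-PCR and/or symptomatic disease, with no minimum interval from the dose. Section 15.1 asks at interim whether AZD7442 prevents infection in the first 6 months.

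**The concern.** Pre-exposure prophylaxis cannot be said to have failed against an infection acquired before it was given. As the definitions stand, such an infection is a breakthrough like any other. Section 1.3 names only two explanations for a breakthrough, failure of the drug and T-cell dysfunction, so an infection that predates the dose would be read as one or the other.

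All patients receive AZD7442, so no control arm carries the same background of incubating infections. Absolute incidence is raised with nothing to offset it. This matters most for the interim question in 15.1, because the follow-up is shorter and section 21.1 links the interim to committee recommendations on redosing.

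A second problem concerns the analyses that relate infection to drug level or T-cell function. The first serum level and the first T-cell assay are both at Day 30. An infection before then has no drug level or T-cell value from before the event.

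**Working it through.** **1. Can screening detect an incubating infection?** RT-PCR is reached only through a positive antigen test. It can therefore clear an antigen-positive patient but cannot find an antigen-negative patient who carries virus. The symptom criterion does not act on someone without symptoms. Exposure is the remaining indicator, and it is not asked about.

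**2. When does counting start?** Baseline is Day 1. Sections 14.1, 17.8 and 17.10 count from baseline or treatment with no lag. That counting starts on Day 1 is an inference from this wording, but no section suggests otherwise. Section 20.1 has the events committee judge SARS-CoV-2 relatedness and severity; it states no task of dating acquisition against the dose.

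**3. The cited post-exposure trial (STORM CHASER, section 23.5).** The counts are 23/749 on drug and 17/372 on placebo.
- Risks: 23/749 = 3.07% and 17/372 = 4.57%.
- Relative reduction: 1 − (23/749)/(17/372) = 32.8%, which reproduces the stated 33%.
- A crude Wald interval on the log risk ratio is −24% to 64%, against the stated −26 to 65. The small gap would fit a model-based interval.

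The same section gives 73% (27 to 90) in participants PCR negative at dosing. Within that group, post hoc, the reduction was "by 51% (95% CI: -71, 86) up to seven days following dosing", against 92% (32 to 99) later. The direction is what early or pre-existing infection would produce.

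**4. Possible size, on assumptions that are not in the protocol.**
- Count: suppose 0.1% to 2% of patients are incubating at the first dose and screening misses 50% to 100% of them. The lowest count is 1,500 × 0.001 × 0.5 = 0.75 and the highest is 1,500 × 0.02 × 1 = 30. For the 750 interim patients the range is 0.4 to 15.
- Share of all infections: let *w* be an incubation window of 3 to 7 days, *m* the fraction missed (0.5 to 1), *VE* the protection after dosing (77% to 83%, the pre-exposure figures in 23.5) and *T* the follow-up in days. With constant infection pressure and no drug effect on infections already incubating, share = *wm* / (*wm* + (1 − *VE*)*T*).
- At *T* = 360: 1.5/(1.5 + 0.23 × 360) = 1.8%, up to 7/(7 + 0.17 × 360) = 10.3%.
- At *T* = 180: 1.5/(1.5 + 0.23 × 180) = 3.5%, up to 7/(7 + 0.17 × 180) = 18.6%.

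These figures show only why six months is more exposed than twelve. Lower protection than 77% would make the share smaller.

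**5. Timing of blood draws.** Section 9.3 places the post-infection draw about 10 days after a positive test. A positive test before about Day 20 therefore leads to a draw before Day 30 (20 + 10 = 30), so the draw precedes the reference from which change is measured. A positive test between Day 20 and Day 30 has its Day 30 reference taken after infection. Either way, the change-from-Day-30 endpoints in section 16.1 have no pre-infection reference. In section 14.3, the comparison of levels collected before the event has no level to use.

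**The case against.** Several counter-arguments stand.

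- **Not a breach of a protocol rule.** Section 23.5 is background. A reader might take section 12.1, "AZD7442 600 mg IM will be administered according to FDA approved guidelines for administration", as importing the exposure condition into eligibility. That sentence sits under dosage and administration and most naturally concerns how the drug is given. What remains is a gap between eligibility and a condition the protocol itself reports.
- **Current infection is largely screened.** The antigen test and the symptom, respiratory-infection and 90-day exclusions remove some cases. Only antigen-negative, symptom-free incubation is left.
- **The post-exposure trial cannot size the effect here.** A reader might infer that protection in this study would be cut from 73% to 33%. Those are reductions against placebo in unvaccinated, known-exposed adults. The intervals are wide and overlap, and the Day 7 split is post hoc. This study requires vaccination and has no placebo arm. Nor does it help to apply that trial's attack rate to an assumed exposed fraction *f* and divide by the same rate in all 1,500: (1,500 × *f* × 3.07%)/(1,500 × 3.07%) = *f*, so the answer is the assumption restated.
- **Group comparisons.** Nothing in the protocol suggests that incubating infections differ by cancer type or therapy. An equal excess in each group leaves a risk difference unchanged and draws a risk ratio towards one.
- **The analysis plan or adjudication manual, neither at hand, could set an at-risk window.** They could. They cannot recover an exposure history that was never taken.
- **A Day 7 cut does not supply a drug level** for infections from Day 8 to Day 30. This is correct, and they need separate handling.

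**Conclusion.** The point holds in a limited form. The protocol cites a no-recent-exposure condition, collects nothing on exposure, cannot detect antigen-negative incubation at entry, and defines breakthroughs so that these infections are included.

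The number is unknown and probably modest. The ranges in the working rest on assumed incubation and detection rates and should not be quoted as estimates. The cited trial gives qualitative support only.

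The primary endpoint, serum concentration, is untouched. The results affected are the interim prevention question, absolute infection incidence, time to first event, and the analyses linking infection to drug level or to change from Day 30. A reader might infer that the breakthrough rate will be seriously distorted or that patients are dosed against a binding rule; the protocol supports neither. This is an inexpensive improvement to interpretability, not a defect that invalidates the study.

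**What to change.** 1. Record known recent exposure at screening, with its date, since section 23.5 leaves recent undefined. Add a sensitivity analysis of infection incidence and time to first event without exposed patients. This part must be collected prospectively.
2. In sections 14.1, 15.1 and 17.10, keep the from-baseline count, list infections with onset in Days 1-7 after the first dose separately, and add a pre-specified sensitivity analysis of infections after Day 7. The cut is the one already used in section 23.5.
3. State that infections before the Day 30 draw have no pre-infection drug level and no valid Day 30 reference. Handle them separately in the concentration-infection and change-from-Day-30 analyses.
4. Reconcile sections 8.1 and 8.2 with the exposure condition reported in section 23.5. Which clinical rule should apply is for the sponsor and investigators.

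The cost is one screening question, slightly more analysis, and a few fewer events in the sensitivity analyses. No new test is needed, and the from-baseline result is retained.
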